- 2. Study visit 2: Injection #1, week 0: FULL PHOTO EVALUATION AND SURVEY #1
- 3. Study visit 3: Injection #2, week 4
- 4. Study visit 4: Injection #3, week 8: FULL PHOTO EVALUATION
- 5. Study visit 5: Injection #4, week 24: FULL PHOTO EVALUATION AND SURVEY #2
- 6. Study visit 6: final assessment visit only, no injections, week 40: FULL PHOTO EVALUATION AND SURVEY #3

At each injection visit (weeks 0,4,8,24) the participant will first speak to the doctor and discuss any adverse reactions. Photographs will be taken as mentioned above. On certain visits, as listed, patient surveys will be given to subjects to assess PRP, any improvements in the alopecia, pain or other adverse effects. The data from these surveys will be used in the final stages of the research to look at patient aggregated data. After this, the injection protocol will be followed as detailed above and the patient will be scheduled for their next appointment.

Patients will be contacted within 12-24 months post study to be informed of results of the study. If possible and if published by this time, a copy of the paper outlining the trial will also be provided to patients.

Primary endpoint:

Photographs of the scalp (with standard digital camera) and trichoscopy photographs (with specialized camera called folliscope to visualize hair follicles and measure hair thickness, density, and caliber where the follicle exits the scalp) will be used for primary evaluation endpoint.

Secondary endpoint:

Additionally, surveys as detailed above will provide qualitative participant information regarding improvement with procedure, pain or other adverse effects.

Subject Selection:

Inclusion Criteria

- 1. Must understand and voluntarily sign an informed consent form
- 2. Must be female between the ages of 18 and 65 years at the time of consent
- 3. Must be able to adhere to the study visit schedule and other protocol requirements
- 4. Documented baseline blood work either in chart review or documented by the hair loss clinician- blood work needed includes normal TSH and ferritin as per the laboratory standards, platelet count above 150,000 platelets per microliter and a negative pregnancy test for any premenopausal women—all blood work must be documented as normal within 12 months prior to the start of the study

Exclusion Criteria

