- -systemic effects, including nausea, fatigue, malaise, flu-like symptoms, headache, runny nose, diplopia, dysarthria, generalized muscle weakness, asthenia, blurry vision, ptosis, dysphagia, dystonia, urinary incontinence, breathing difficulties, rash.

Prior And Concomitant Medications:

At the initial visit, prior and concomitant medications and therapies will be reviewed as may pertain to exclusion from the study.

Restricted Medications/Treatments:

The restricted medications and treatments prior to the study initiation are those that the investigator feels may indicate that the patient has an unstable medical condition, as described in the exclusionary criteria.

Subject Withdrawal Or Discontinuation:

Subjects may choose to withdraw from the study or may be withdrawn by the investigator at any time without prejudice to their future medical care. Any subject who does not comply with the inclusion/exclusion criteria may be withdrawn from further participation in the study.

Discontinuation Procedures:

Any subject who wishes to discontinue prematurely from the study should return to the study center for an End of Study Visit.

Adverse Event Definitions:

An adverse event (AE) is any untoward medical occurrence in a patient or clinical investigation subject which is temporally related to protocol procedures, including administration of a

pharmaceutical product at any dose, but which does not necessarily have a causal relationship with the treatment. The term AE also applies to laboratory findings or results of other diagnostic procedures that are considered to be clinically relevant (e.g., that required unscheduled diagnostic procedures or treatment measures or result in withdrawal from the study). Surgical procedures themselves are not adverse events; they are therapeutic measures for conditions that require surgery. The condition for which the surgery is required is an adverse event, if it occurs or is detected during the study period. Planned surgical measures permitted by the clinical study protocol and the condition(s) leading to these measures are not adverse events, if the condition(s) was (were) known before the start of study treatment.

Adverse events will be recorded according to CTCAE guidelines.

A serious adverse event (SAE) is any AE or adverse drug reaction that at any dose results in any of the following outcomes:

- death
- life-threatening adverse event
- inpatient hospitalization or prolongation of existing hospitalization

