**The Effect of Platelet Rich Plasma on Non-scarring Alopecia**

**PI: [name]**

**NCT03689452**

**Document Date: 9/21-2018**

**The Effect of Platelet Rich Plasma on Non-scarring Alopecia:  
A Randomized, Controlled Clinical Trial**

**PI:** [name]

**Date:** 9/21/18

*Statistical analyses*

Statistical analyses will be performed using SAS version 9.4 (SAS Institute Inc., North Carolina, United States). Difference scores from baseline to week 8 and from baseline to week 24 will be calculated for both hair density and caliber. The PRP and saline groups will be compared on these difference scores using independent samples t-tests. The difference scores will also be dichotomized based on whether the change over time was positive or negative. The PRP and saline groups will be compared on these dichotomized scores using chi-square tests. All given p-values will be two tailed and a p-value of less than 0.05 will be regarded as indicating statistical significance.

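### With no missing-data rule, a woman who leaves between weeks 8 and 24 falls out of the week-24 tests by default, and her recorded week-8 change goes unused

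*Protocol*

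**What the plan says.** The protocol's Subject Withdrawal Or Discontinuation section lets women leave, or be withdrawn, at any time: "Subjects may choose to withdraw from the study or may be withdrawn by the investigator at any time without prejudice to their future medical care". Discontinuation Procedures then gives the only follow-up rule: "Any subject who wishes to discontinue prematurely from the study should return to the study center for an End of Study Visit". The timing of that visit, whether folliscope images are taken at it, and whether a woman may stop injections but stay for imaging are all left open.

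The Protocol Schedule places full photo evaluations at weeks 0, 8, 24 and 40. The two that matter here are "Study visit 4: Injection #3, week 8: FULL PHOTO EVALUATION" and "Study visit 5: Injection #4, week 24: FULL PHOTO EVALUATION AND SURVEY #2".

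The SAP states: "Difference scores from baseline to week 8 and from baseline to week 24 will be calculated for both hair density and caliber". On the test it says: "The PRP and saline groups will be compared on these difference scores using independent samples t-tests". The same scores, split into positive and negative change, go to a second comparison: "The PRP and saline groups will be compared on these dichotomized scores using chi-square tests". Neither document states an analysis population, a missing-data method, a visit window, or a rule for placing an exit-visit image.

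**The concern.** Week 24 is the latest time point the SAP analyses, and density and caliber are among the primary-endpoint measures. A t-test on the week-24 difference score can use only women who have a week-24 value. If leaving is related to early response, the women left at week 24 are a selected group. If that selection differs between arms, the comparison of completers no longer estimates the effect in the women randomised. The week-8 change carries information about those who left, and it will already have been collected. A separate t-test at each visit ignores it. With no rule written down, the handling of these women would also be chosen after the data are seen.

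**Working it through.** **1. The gap.** Scheduled imaging is at weeks 0, 8, 24 and 40, and 24 − 8 = 16 weeks. A woman who leaves in that interval has week-0 and week-8 images and so a week-8 score, but no scheduled week-24 image. She contributes to the week-8 tests. By default she is absent from the week-24 t-tests for density and caliber and from the matching chi-square tests.

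**2. No figure to reproduce.** The documents give no sample size, SD, effect size or dropout rate. Everything below is assumption.

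**3. Assumptions for bias.**
- 30 women per arm; true week-24 effect 0.60 SD.
- Week-8 effect 0 to 0.5 SD; correlation ρ of week-8 with week-24 change 0.5 to 0.85.
- A poor responder is in the lowest 40% of week-8 change, both arms pooled. She leaves with probability p = 0.3 to 0.5; others leave with probability 0.05.

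Let z be the 40% cut-off in an arm's own SD units, F = Φ(z) and φ the normal density at z. Then:
- dropout D = F·p + (1 − F)·0.05
- shift in that arm's completer mean at week 24 = ρ·m, where m = φ·(p − 0.05)/(1 − D)

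**4. Rule differs by arm** (saline as above; PRP dropout 0.10 regardless of response, so no PRP shift).
- Mild end: no week-8 effect, p = 0.3, ρ = 0.5. Here z = −0.253, F = 0.40, φ = 0.3863. D = 0.40 × 0.3 + 0.60 × 0.05 = 0.15. m = 0.3863 × 0.25/0.85 = 0.114. Shift = 0.5 × 0.114 = 0.057. Difference = 0.60 − 0.057 = 0.543, which is 9.5% too small.
- Severe end: week-8 effect 0.5, p = 0.5, ρ = 0.85. Solving 0.5Φ(z) + 0.5Φ(z − 0.5) = 0.40 gives z = −0.011, F = 0.4955, φ = 0.3989. D = 0.4955 × 0.5 + 0.5045 × 0.05 = 0.273. m = 0.3989 × 0.45/0.727 = 0.247. Shift = 0.85 × 0.247 = 0.210. Difference = 0.390, which is 35% too small.

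**5. Same rule in both arms.**
- No week-8 effect: both arms shift equally and the bias is 0.
- Week-8 effect 0.5, p = 0.5, ρ = 0.85: in the PRP arm z = −0.511, F = 0.3045, φ = 0.350, D = 0.187, m = 0.350 × 0.45/0.813 = 0.194. Net bias = 0.85 × (0.247 − 0.194) = 0.045. Difference = 0.555, which is 7.5% too small.

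**6. Simulation at 30 per arm** agrees, with a little Monte Carlo scatter:

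| Dropout rule | Saline / PRP dropout | Completers' difference | Bias |
|---|---|---|---|
| Same in both arms | similar | about 0.55–0.60 SD | about 0–9% |
| Differs by arm | about 15–28% / 10% | about 0.39–0.54 SD | about 10–36% |

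An estimate that uses the week-8 change averages about 0.60 throughout. That is expected, because leaving was generated from that same observed change.

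**7. Precision.** With uninformative dropout d equal in both arms, the completers' variance relative to full data is 1/(1 − d). Using week 8 it is ρ² + (1 − ρ²)/(1 − d). At d = 0.2 and ρ = 0.7 these are 1.25 and 0.49 + 0.51/0.8 = 1.1275, a standard error ratio of √(1.1275/1.25) = 0.95. Starting from an assumed 80% full-data power, completers have 75.7%, 70.7% and 65.0% at 10%, 20% and 30% dropout. Using week 8 gives 76.8–79.2%, 72.9–78.2% and 68.3–76.9% for ρ from 0.5 to 0.9. The gain is modest.

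**The case against.** Four objections deserve an answer.

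- **Silence is not a prohibition.** A reader might infer that the protocol forbids a woman to decline injections and keep her photo visits, or that an exit image can never count as week 24. Neither is stated. The exit visit could fall near week 24, and no window rules it in or out. This stands. The defect is that the handling is unspecified and that a t-test drops missing values by default.
- **Reasons for leaving are unknown.** A reader might infer that women who see no benefit will leave to start standard hair drugs, because recent use is an exclusion. That exclusion and the restricted-medications section both concern the time before the study. Neither says a woman must leave to start such a drug, and neither document gives an expected reason for dropout. This stands, and nothing here relies on it.
- **The larger bias needs an arm-specific rule.** The protocol uses goggles, a sham needle placement and the same preparation delay in both arms. If that masking works, women with the same visible response should leave at similar rates, and the 0–9% range applies. This stands, and that range should be read first.
- **Size and direction.** At 30 per arm the standard error of the completers' difference is about 0.28 SD, larger than any bias shown. In these scenarios the bias runs against PRP, so it does not manufacture a benefit. That is fair, but the direction follows from which arm is assumed to lose its poor responders, and it would reverse if the PRP arm did.

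It is also fair that women act on perceived change and that no survey is scheduled at week 8. The folliscope change may therefore not fully explain leaving, so the model reduces the problem without guaranteeing its removal.

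**Conclusion.** The concern holds as a gap in the plan that is cheap to close. Women who leave between weeks 8 and 24 are by default absent from the week-24 tests, and their week-8 change is not used. Under the stated assumptions the bias is about 0–9% with one dropout rule for both arms. It is about 10–36% only if poor responders leave the saline arm more often. The documents do not support treating the upper range as the expected size, because they give no dropout rate and no sign that leaving will differ by arm. The correction is about unbiased only when leaving depends on the observed week-8 change, and its standard error is only slightly smaller. The main gains are protection against selective loss and a missing-data approach fixed in advance.

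**What to change.** 1. **SAP, Statistical analyses.** Replace the separate t-tests with one repeated-measures mixed model each for density and caliber. The outcome is change from week 0 at weeks 8 and 24; week 40 may be added because it is already photographed. Include visit, arm by visit, week-0 value by visit and an unstructured covariance, for all randomised women with any post-baseline image. Take the week-8 and week-24 arm contrasts from the model, and add a brief missing-not-at-random sensitivity analysis. The model does not repair the dichotomised chi-square comparison, so label that as an analysis of women with the visit's image.
2. **Protocol, Discontinuation Procedures.** State that a woman who stops injections is asked, without affecting her right to withdraw, to attend the remaining scheduled photo visits for imaging only.

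Cost: SAP wording and a procedure available in the SAS release already named, a short protocol amendment, and some retention effort. No new visit dates are needed. The downside is reliance on a missing-at-random assumption, which the sensitivity analysis is there to probe.

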**The Effect of Platelet Rich Plasma on Non-scarring Alopecia**

**PI: [name]**

**NCT03689452**

**Document Date: 9/21-2018**

**The Effect of Platelet Rich Plasma on Non-scarring Alopecia:  
A Randomized, Controlled Clinical Trial**

**PI:** [name]

**Date:** 9/21/18

*Statistical analyses*

Statistical analyses will be performed using SAS version 9.4 (SAS Institute Inc., North Carolina, United States). Difference scores from baseline to week 8 and from baseline to week 24 will be calculated for both hair density and caliber. The PRP and saline groups will be compared on these difference scores using independent samples t-tests. The difference scores will also be dichotomized based on whether the change over time was positive or negative. The PRP and saline groups will be compared on these dichotomized scores using chi-square tests. All given p-values will be two tailed and a p-value of less than 0.05 will be regarded as indicating statistical significance.

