The Effect of Platelet Rich Plasma on Non-scarring Alopecia

PI: [name]

NCT03689452

Document Date: 9/21-2018

The Effect of Platelet Rich Plasma on Non-scarring Alopecia: A Randomized, Controlled Clinical Trial

Identifiers: GCO: 18-1714 IF2274490

IRB: IRB-18-00297

Investigators: [name] [name] [name] [name]

Study Site:
Mount Sinai School of Medicine
Department of Dermatology

New York, NY 10028

Financial Support:

Eclipse

Protocol Version: 2

Date: 9/21/18

The Effect of Platelet Rich Plasma on Non-scarring Alopecia: A Randomized, Controlled Clinical Trial

Introduction and rationale:

The purpose of this study is to evaluate the clinical efficacy of platelet rich plasma (PRP) injections for non-scarring alopecia in women. A randomized, placebo-controlled clinical trial will be performed where patients with non-scarring alopecia will either receive injections of their own PRP or injections of normal saline (placebo). Patients in the treatment group (Group A) will have a small amount of their own blood drawn (22 mL) and have their PRP injected into their scalp. The injections will be given at weeks zero, four, eight, and twenty-four. The number of injections in the PRP group will vary slightly based on how much PRP is able to be extracted from the patients' blood. However, typical number of injections will range from 10-30 with 0.2 mL injected into each site. The placebo group (Group B) will be given the same schedule but will receive sham injections only composed of normal saline (3 mL, total of 15 injections with 0.2 mL in each injection site). In place of the blood draw, the placebo group will have a sterile needle placed into the ante-cubital fossa but no blood will be taken from the patient. Both groups will have clinical data collected at all visits, including a screening visit before enrollment and a final assessment visit at week 40, for a total of six study visits per patient. Data collection will include representative photographs of the scalp and measurements of hair thickness using a specialized camera called a folliscope as well as a standard digital camera for macroscopic photos. No hair samples will be needed for photographs and there will be no biopsies taken during this study. The results from the two groups will then be compared. Patients will also be given small surveys at the beginning, middle and end of the study to assess for any pain, adverse effects, and the level of improvement the subjects have seen.

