In summary, all study participants will have a screening visit before enrollment, 4 study visits for subdermal scalp injections, and one final assessment visit at week 40. Data analysis and comparison will be measured with macroscopic photography and microscopic hair follicle photography as well as with patient surveys.

Objective:

To evaluate the clinical efficacy of platelet rich plasma (PRP) injections for non-scarring alopecia in women .

Description of Study:

Subjects receiving PRP injection will undergo the following protocol:

All subjects will be asked to wear dark, non-visible goggles during the blood draw in the beginning of the visit. 22 mL of whole blood will be drawn from a peripheral vein and then processed through a centrifuge two times thus obtaining about 3-6 mL of plasma rich in leukocytes and platelets. The doctor will leave the room for approximately 10 -15 minutes to prepare the PRP injections. The subject's scalp will be cleansed topically with alcohol and then injected with the patient's PRP using a 25-gauge needle in a 3 mL Luer-lock syringe into the subcutaneous scalp. Injections will be 1-2 cm part and the amount injected will be 0.2 mL per injection. The number of injections in the treatment group will vary from patient to patient depending on the amount of PRP that was able to be harvested from the blood draw. However,

patients can expect anywhere from 10-30 injections. There will not be more than 30 injections in any patient during any study visit.

Subjects receiving placebo (preservative-free normal saline) will undergo the following protocol: All subjects will be asked to wear dark, non-visible goggles during the blood draw period in the beginning of the visit. The patient in the control group will have a sterile needle placed by a certified doctor or medical assistant into the ante-cubital fossa of the arm but no physical blood will be taken out of the patient. The doctor will leave the room for approximately 10 -15 minutes to prepare the normal saline injections. The subject's scalp will be cleansed topically with alcohol and then injected with 0.9% normal saline, for a total of 3 mL, (0.2 mL in each injection site and 15 total injections). The injection sites will be 1-2 cm apart.

Protocol Schedule:

- 1. Study visit 1: screening visit with the clinical research team after referral from Hair loss clinic with prior baseline blood work already reviewed

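### The protocol schedules full photography at week 40, after all four injections, but the SAP tests hair density and caliber only at weeks 8 and 24

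*SAP*

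**What the plan says.** **SAP, Statistical analyses.** The change scores are defined at two visits only: "Difference scores from baseline to week 8 and from baseline to week 24 will be calculated for both hair density and caliber". These scores are compared between the two arms by t-test and, after splitting them into positive and negative change, by chi-square test. Each test is two-sided at 0.05. Week 40 does not appear, and no reason is given for leaving it out.

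**Protocol, Introduction and rationale.** Collection runs to the last visit: "Both groups will have clinical data collected at all visits, including a screening visit before enrollment and a final assessment visit at week 40". On what is collected, it says: "Data collection will include representative photographs of the scalp and measurements of hair thickness using a specialized camera called a folliscope". It then adds: "The results from the two groups will then be compared". The summary at the end of the section lists "4 study visits for subdermal scalp injections, and one final assessment visit at week 40", followed directly by: "Data analysis and comparison will be measured with macroscopic photography and microscopic hair follicle photography as well as with patient surveys".

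**Protocol, Protocol Schedule.** Full photo evaluations are set for weeks 0, 8, 24 and 40. The last entry reads: "Study visit 6: final assessment visit only, no injections, week 40: FULL PHOTO EVALUATION AND SURVEY #3". The paragraph under the schedule puts the photographs before the injection at each injection visit.

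**Protocol, Primary endpoint.** Scalp photographs and trichoscopy are primary; the folliscope is there to "measure hair thickness, density, and caliber where the follicle exits the scalp) will be used for primary evaluation endpoint". No visit is named.

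**Protocol, Data Analysis.** One general sentence says that efficacy variables, their sum and safety parameters will be analyzed. It gives no visit and no test.

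**The concern.** Read together, the protocol's statements foresee a comparison of the groups on photography that includes the final visit. The SAP, which carries the same date, stops at week 24.

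The omitted visit is the only photo evaluation that follows the whole scheduled course. The objective is the clinical efficacy of PRP injections, and the schedule has four. If the SAP is followed exactly, no density or caliber test speaks to the full course, and none shows whether a difference seen earlier is still there at the end of the study.

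The investigators could still analyze week 40 later. Whether to report it would then be decided with the data in hand, and the result could not carry the weight of a prespecified one.

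**Working it through.** The documents give no sample size, power, effect size or dropout rate, so there is no design figure to reproduce. The check is a count from the schedule and the SAP.

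**1. Injection visits before each reading.** Injections are at weeks 0, 4, 8 and 24. Photographs precede that day's injection.

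| Full photo evaluation | Injection visits already completed | Number | Density and caliber test in SAP |
|---|---|---|---|
| Week 0 | none | 0 | baseline |
| Week 8 | 0, 4 | 2 | yes |
| Week 24 | 0, 4, 8 | 3 | yes |
| Week 40 | 0, 4, 8, 24 | 4 | none |

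Density and caliber are therefore tested at 2 of the 3 post-baseline evaluations, and no tested reading follows all four injection visits.

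**2. Follow-up without a specified test.** 40 − 24 = 16 weeks, and 16/40 = 40% of follow-up. This restates the same missing visit in time units; it is not a second deficiency.

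**3. Number of tests.** Count = visits × outcomes × methods.
- Now: 2 × 2 × 2 = 8, of which 0 use week 40.
- With week 40 added in the same form: 3 × 2 × 2 = 12.

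**4. Cost in false positives if nothing else changes.** If every test could support a claim at 0.05 and the tests were independent, the chance of at least one false positive would be 1 − 0.95^k.
- All tests: k = 8 gives 33.7%; k = 12 gives 46.0%.
- t-tests alone: k = 4 gives 18.5%; k = 6 gives 26.5%.

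Independence is an assumption. These tests are correlated, so the figures are illustrative and on the high side. The finding does not depend on them; they show why the remedy should include a named primary test.

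**5. What a week-40 test would show.** Week 40 against baseline compares the groups after the whole course, 16 weeks after the last injection (40 − 24). The week-24 reading also comes 16 weeks after the preceding injection (24 − 8). Setting week 40 against week 24 would not isolate the fourth injection, because the spacing of injections and the total elapsed time also differ.

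**The case against.** The strongest reply is that no sentence promises a week-40 test of density or caliber. The comparison statements name neither a visit nor a test, the primary endpoint has no time point, and an SAP may test a subset of the scheduled assessments. The Introduction is also a loose summary: taken literally, it would call for data at screening and week 4 too, where the schedule sets no full photo evaluation. This stands to the extent that the finding is an unexplained omission, not a breach of a stated primary time point. It does not remove the omission. The schedule itself provides a full photo evaluation at week 40, nothing limits the comparison to earlier visits, and neither document gives a reason.

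Second, the Data Analysis section leaves room for a descriptive week-40 analysis. That is correct, so the accurate statement is that week 40 has no specified density or caliber test, not that it is barred from analysis.

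Third, a reading 16 weeks after the last injection mixes the effect of the full course with any waning, and cannot separate the two. This is a fair limit on interpretation. The week-24 reading has the same interval after its preceding injection, so it is not a reason to test one visit and omit the other.

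Fourth, standard photographs and hair thickness also belong to the primary endpoint and have no named test at any visit. For that reason the counts here refer to density and caliber only.

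Fifth, more tests mean more chances of a false positive. That is true if all are treated as equal, and the remedy deals with it.

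**Conclusion.** The concern holds and should be fixed. None of the 8 planned tests uses week 40, density and caliber are tested at 2 of 3 post-baseline photo evaluations, and no tested reading follows all four injection visits.

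This is a gap in what is tested, not a bias. The week-8 and week-24 comparisons remain valid randomized comparisons of the effect after two and three injection visits. The conclusion rests on the text of the two documents and on photographs preceding the injection at each injection visit, as the schedule paragraph describes. It uses no assumed figure, and it does not require week 40 to be primary.

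**What to change.** 1. Add the baseline-to-week-40 differences in hair density and caliber to the SAP, compared between groups by the methods already stated. The two t-tests alone would close the main gap if the investigators prefer not to extend the dichotomized analysis.
2. Name in advance one primary visit, outcome and test, and label all others secondary. That one test stays at 0.05, and going from 8 to 12 tests adds no further chances to claim success.
3. If week 24 is kept as primary, describe it as the effect after three injections and make week 40 a prespecified secondary.
4. If week 40 is deliberately left untested, say so in the SAP and give the reason. This removes the ambiguity but leaves the full course untested.

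The cost is SAP wording and at most four more tests. The week-40 images are already scheduled, so no visits, procedures or patients are added. Precision at week 40 may be lower because of dropout, by an amount the documents do not allow to be estimated.

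### The t-tests on change scores fix the baseline slope at 1; ANCOVA on the same week-0 value would usually be more precise and would deal better with chance baseline differences

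*SAP*

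**What the plan says.** The SAP's Statistical analyses section is one paragraph. For the continuous outcomes it states: "Difference scores from baseline to week 8 and from baseline to week 24 will be calculated for both hair density and caliber". It then states: "The PRP and saline groups will be compared on these difference scores using independent samples t-tests". The significance rule is: "All given p-values will be two tailed and a p-value of less than 0.05 will be regarded as indicating statistical significance".

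Baseline therefore enters these comparisons only by subtraction. Neither document mentions a baseline covariate, a regression model, or stratification on baseline density or caliber. The protocol's Data Analysis section is a single general sentence and names no method.

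The covariate would already be collected. The Protocol Schedule lists "Study visit 2: Injection #1, week 0: FULL PHOTO EVALUATION AND SURVEY #1", and the Primary endpoint section says the folliscope is used to "measure hair thickness, density, and caliber where the follicle exits the scalp".

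**The concern.** A t-test on change scores is a baseline-adjusted comparison in which the regression slope of follow-up on baseline is set to 1 instead of being estimated. The true slope is the baseline-to-follow-up correlation times the ratio of follow-up SD to baseline SD. If the SDs are equal and the correlation is below 1, the slope is below 1.

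Two things follow:

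- **Precision.** The treatment difference is usually estimated less precisely than the same measurements allow, so confidence intervals are wider and power is lower.
- **Chance imbalance.** Because allocation is randomized, any baseline difference between arms is due to chance. With a slope below 1, the change score removes too much of it and pushes the estimate in the opposite direction. This averages out over repeated trials, but not within the one trial that is run.

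This is a question of efficiency and of bias conditional on the observed imbalance. It is not an error in the test.

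**Working it through.** **Inputs from the documents.** Outcomes are density and caliber, changes are taken at weeks 8 and 24, the test is an unadjusted two-sample t-test, and alpha is 0.05 two-sided (all from the SAP). Week 0 is the only scheduled full photo evaluation before treatment (Protocol Schedule). The plan states no power or sample size figure, so there is none to reproduce.

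**Assumed inputs.** 1:1 allocation, n = 10, 20 or 30 per arm, correlation rho = 0.5, 0.7 or 0.9 (0.95 as an extreme), normal data, and equal SDs unless stated.

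**Step 1: large-sample variance.** Let s0 and s1 be the baseline and follow-up SDs. Per arm:

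- Var(change) = s0² + s1² − 2·rho·s0·s1
- Var(ANCOVA) = s1²(1 − rho²)
- The difference is (s0 − rho·s1)², which is never negative and is zero only when the slope rho·s1/s0 equals 1.

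With equal SDs the ratio ANCOVA/change is (1 + rho)/2, which is 0.75, 0.85 and 0.95 at rho 0.5, 0.7 and 0.9.

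**Step 2: cost of estimating the slope.** For a normal covariate, multiply the ratio by (2n − 3)/(2n − 4), which is 17/16, 37/36 and 57/56 at n = 10, 20 and 30. Setting the product to 1 gives the break-even correlation, 2(2n − 4)/(2n − 3) − 1. Power is from the noncentral t, at the effect for which the change-score t-test has 80%.

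| n per arm | Variance ratio at rho 0.5 / 0.7 / 0.9 | Break-even rho | ANCOVA power at rho 0.5 / 0.7 / 0.9 |
|---|---|---|---|
| 10 | 0.797 / 0.903 / 1.009 | 0.882 | 88% / 84% / 79% |
| 20 | 0.771 / 0.874 / 0.976 | 0.946 | 89% / 85% / 81% |
| 30 | 0.763 / 0.865 / 0.967 | 0.965 | 89% / 85% / 81% |

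**Step 3: unequal SDs.** With k = s1/s0, the large-sample ratio is k²(1 − rho²)/(1 + k² − 2·rho·k). At rho 0.8:

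- k = 1.25: slope 0.8 × 1.25 = 1, and the ratio is 0.5625/0.5625 = 1.00, so there is no gain.
- k = 0.8: slope 0.8 × 0.8 = 0.64, and the ratio is 0.2304/0.36 = 0.64.

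**Step 4: shift from a chance imbalance.** With equal SDs, the change-score estimate moves by −(1 − rho) times the baseline difference. A baseline difference of one standard error is sqrt(2/n) SD, or 0.316 SD at 20 per arm. The size of the shift is then 0.158, 0.095 and 0.032 SD at rho 0.5, 0.7 and 0.9. As a fraction of the change-score estimate's own standard error it is sqrt((1 − rho)/2), which is 0.50, 0.39 and 0.22.

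**Step 5: simulation check** (40,000 trials per cell, n = 10, 20 and 30, rho 0.5 to 0.95). Type I error was 0.047–0.054 for the t-test and 0.047–0.053 for ANCOVA. Simulated ANCOVA power at rho 0.5, 0.7 and 0.9 was 0.877, 0.835, 0.795 (n = 10), 0.892, 0.849, 0.806 (n = 20) and 0.893, 0.853, 0.811 (n = 30), in line with the table. At n = 20 the average CI width ratio ANCOVA/t-test was 0.879, 0.935 and 0.988 at rho 0.5, 0.7 and 0.9, and 1.002 at rho 0.95.

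**The case against.** The strongest reply is that the plan already uses baseline and chooses between two valid methods, and that nothing in the documents places this trial where the gain is large. The variance ratio ranges from 0.64 to slightly above 1 over reasonable assumptions, and at rho 0.9 the change in power is only about −0.5 to +1 point. Within a single trial the benefit is less certain than the averages suggest. In simulation with equal SDs, the ANCOVA interval was the narrower one in the following share of trials:

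| n per arm | rho 0.5 | rho 0.7 | rho 0.8 | rho 0.9 |
|---|---|---|---|---|
| 10 | 80% | 63% | 50% | 36% |
| 20 | 96% | 85% | 72% | 52% |
| 30 | 99% | 94% | 85% | 64% |

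These counts stand. They mark where the advantage runs out: very small arms with high correlation. They do not reverse the conclusion, because the stakes are unequal. In the equal-SD settings the worst loss is about 1 to 2 points of power (10 per arm, rho 0.9 to 0.95), against a gain of about 4 to 9 points at rho 0.5 to 0.7. They also leave the chance-imbalance argument untouched.

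Three smaller points were raised:

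- **Baseline is not defined in the SAP.** The protocol's Introduction also mentions data collection at screening. Week 0 is the only scheduled pre-treatment full photo evaluation, so the reading is sound; naming week 0 in the model settles it.
- **The model must be fixed before outcomes are seen.** This is right, and writing it into the SAP in time does so.
- **The sign-of-change chi-square tests also depend on baseline.** This is true, but they are separate analyses that this change leaves as they are.

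**Conclusion.** The concern holds, as a recommended improvement to a valid analysis. Neither document plans baseline as a covariate, and the change-score t-test gives up precision whenever the true slope is materially different from 1.

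Under equal SDs and rho 0.5 to 0.7, the variance falls by roughly 10% to 24% at 10 to 30 per arm (ratios 0.903 to 0.763). At rho 0.9 the effect lies between a reduction of about 3% and an increase of about 1%. There is no large-sample gain if the slope happens to be 1.

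Confidence in the direction is good except in very small arms with rho near 0.9 or above. Confidence in the size is limited, because sample size, SDs and correlation are all assumed.

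**What to change.** In the SAP, replace each of the four t-tests (density and caliber, weeks 8 and 24) with a linear model of the follow-up value, or equivalently the change, on treatment group, with the week-0 value of the same measure as covariate. Report the adjusted treatment difference with its 95% CI. Keep the t-test on difference scores as a sensitivity analysis. Make the change before outcome data are seen by arm.

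The cost is one sentence in the SAP, a standard SAS linear-model procedure, and one residual degree of freedom per model (2n − 3 instead of 2n − 2). No new data or visits are needed.
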